2.3.3.2 Blood Glucose Level

Blood glucose level will be monitored twice/day for the first 4 days (96 hours), with one measurement approximately 1 hour after the study drug administration each day, and then starting at Day 4 every other day (at 07:00-10:00, before a meal).

The blood glucose level will be summarized using descriptive statistics for each treatment group by time and the day during the treatment period (Day 1 to Day 28), and the 3-month follow-up visit.

A shift table will be provided to summarize the changes from the baseline statuses to the post-baseline statuses.

Graphical presentation of the mean glucose level over time by treatment group will be provided.

A subject data listing of blood glucose level will be provided.

2.3.3.3 Respiration Status

Fraction of inspired oxygen will be summarized using descriptive statistics. The other categorical variables will be summarized as percentages for each treatment group.

Confidential Page 32 of 40

A subject data listing of respiration status will be provided.

2.3.3.4 Complete Blood Count

A subject data listing of complete blood count will be listed.

2.3.3.5 Anti-Insulin Antibodies

A subject data listing of anti-insulin antibodies will be listed.

2.3.4 Vital Signs, Physical Examination Findings

2.3.4.1 Vital Signs

Descriptive statistics for vital signs (diastolic and systolic blood pressure, pulse rate, respiration rate, temperature, weight) and changes from baseline will be presented by visit and treatment group.

Baseline to maximum post-baseline and baseline to minimum post-baseline value shift tables will be generated, as applicable for each parameter and will include subjects with both baseline and post-baseline data.

A subject data listing of vital signs will be provided.

2.3.4.2 Physical Examinations

Physical examination results are collected at screening, each treatment day, the day of discharge, and 3-month corrected age follow-up visits. Each component of the physical examination will be recorded as normal, abnormal not clinically significant, or abnormal clinically significant.

Physical examination results will be summarized by treatment group in frequency and percentage at these visits.

A subject data listing of physical examination will be provided.

2.3.5 Other Safety Analyses

2.3.5.1 Frequency and Consistency of Stool

Data on stools are collected at screening, on treatment days (Days 1-28), the day of discharge, and 3-months follow-up visit for frequency per day, consistency (watery, soft, solid, meconium, or unknown consistency), and bloody stool.

[figure not shown]
The frequency will be summarized using descriptive statistics for each treatment group and by visit. The categorical responses will be summarized by the percentage for each treatment group by visit.

A shift table will be provided to summarize the changes from the baseline statuses to the

Confidential Page 33 of 40

post-baseline statuses.

A subject data listing of stool frequency and consistency will be provided.

Confidential Page 34 of 40

Statistical Analysis Plan V1.3 SAP Date: 06APR2018

3 FUTILITY ANALYSIS AND DATA MONITORING COMMITTEE (DMC)

3.1 FUTILITY ANALYSIS

The study will include an interim futility analysis of the primary endpoint. The interim futility analysis will be performed when at least 150 subjects have been randomized. The date for data transfer, which includes the values for the primary endpoint and the key secondary endpoint, and gestation age group and region (North America, Europe, and Israel) will allow the randomized subjects to be followed for at least 28 days. The multiple imputation for the missing values due to drop-out will be implemented as described in Section 2.2.1.3.1. if more than 10% of values are missing due to early termination other than NEC or death for the primary endpoint. A partial data lock (snap shot) will be completed after the data transfer and the data and SAS program will be transferred to the unblinded statistician to complete the interim futility analysis.

To maintain adequate statistical power for the final analysis of the primary endpoint, a blinded sample size re-estimation will be carried out at the time of the interim futility analysis. The blinded team statistician will calculate the pooled standard deviation of the primary endpoint without distinguishing treatment groups. The sample size may be increased up to 450 patients (total) if the estimated standard deviation is at least 10% larger than that assumed in the sample size section of the protocol. In order to keep the sample size re-estimation independent of the futility analysis, the sample size reestimation will be based on the blinded data used for the futility analysis to obtain the pooled standard deviation. The result of the blinded review will be documented and reported to the sponsor and DMC before the DMC meets to consider futility. The final sponsor decision on sample size will be provided to the DMC and will be the primary driver in the futility assessment. Because the analysis will be based on ranks, a van Elteren test will be used to compare NTRA-2112 to placebo. To calculate sample size, a 2-sample t-test for 85% power to account for the reduced power of the non-parametric test was used (i.e., expect that a t-test with 85% power to have at least 80% power when the van Elteren test is applied). With 144 evaluable patients per arm, assuming a standard deviation of 5.0 days, a 2-sample t-test will have 85% power to detect a mean difference of 1.77 days in the number of days to reach full enteral feeding between the treated and placebo arm. Similarly, assuming a standard deviation of 4.0 days, a 2-sample t-test will have 85% power to detect a mean difference of 1.42 days. Considering a dropout rate of 5%, an enrollment of 152 patients per arm will likely recruit 144 per arm evaluable

Confidential Page 35 of 40

patients.

For the futility analysis, the conditional power of showing statistically significant ($P \le 0.05$) evidence of benefit on the primary endpoint at the final analysis will be calculated for each dose group. Conditional power will be calculated from the z-value based on the interim analysis, treating the primary endpoint as a continuous variable, approximately following the normal distribution. The conditional power will be calculated based on the observed interim trend of effect size, not the original expectation in the sample size calculation. If the conditional power is less than 35% in either dose, continuing to enter infants in that dose group will be considered statistically futile.

The futility analysis results, including the calculated conditional power for each dose group and summaries of selected key safety parameters (adverse events, lab tests, physical exams, and vital signs), will be presented to the Data Monitoring Committee, who will review the results and make a final recommendation regarding the continuation or discontinuation of one or both dose arms. The recommendation will be based on the conditional power and the totality of the clinical data available.

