1.3.3 Sample Size and Statistical Power Considerations

Presentation of sample size is based on the hypothesis that NFE in either treatment group is shorter than in the placebo group. Based on limited historical data (Phase 2), the

Confidential Page 14 of 40

conservative mean is 8.0 days for the placebo group and 6.6 days for each of the 2 active dose groups. This assumes a standard deviation of 3.5 days for each group.

The analysis will be based on a nonparametric test. The NFEs for each infant in the FAS will be ranked from shortest time (the best outcome) to longest time. Infants who do not achieve full enteral feeding and also experience necrotizing enterocolitis (NEC) will be assigned the next set of ranks; all the infants experiencing NEC will be ranked in terms of their time to NEC (the earlier the worse) and will be assigned ranks one greater than the rank of the longest time to achieve NFEs. All infants who do not achieve full enteral feeding and die will be assigned the next set of ranks, again with the earliest deaths assigned the largest (i.e. worst) rank. Thus, each infant who has achieved EN or who has died or suffered NEC will have a recorded rank.

Randomization will be stratified by center and by gestational age group. The statistical analysis will stratify the infants by gestational age group and region (North America, Europe, and Israel), but not by center. Because the analysis will be based on ranks, a van Elteren test will be used to compare NTRA-2112 to placebo. To calculate sample size, an independent groups t-test for 85% power to account for the reduced power of the non-parametric test was used (i.e., expect that a t-test with 85% power to have at least 80% power when the van Elteren test is applied). A two-side 5% test will be used to compare each active dose to placebo. These calculations give N = 115 infants per group. To account for the reduction in power caused by potential missing data, the sample size was increased to 130 per group or a total sample size of 390

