4 SUMMARY OF MAJOR CHANGES IN THE PLANNED ANALYSES

The PP set is defined differently from the protocol, but the difference is not considered to be major. The approach described in the protocol of using methods that separate the reasons for noncompliance from the effect of study drug (e.g. Robins, 1989) will not be followed. Instead, the more common approach of defining a PP set based on study compliance will be adopted. PP analysis will only be supportive of the primary intention-to-treat analysis based on the FAS.

The treatment difference between two NTRA-2112 doses will be estimated for the primary endpoint, key secondary endpoint, exploratory secondary endpoint, and other endpoints.

The Bonferroni correction was described in the protocol for testing the primary and the key secondary endpoints simultaneously for each dose level. Nutrinia believe that insulin as a growth factor will have effect with both doses. We expect that there is an opportunity for exploring higher dose that may yield a more favorable clinical effect than the lower dose that was used in the phase 2. Thus for that reason, a hierarchical approach is now being implemented in the analysis. This procedure is described in Section 1.7 of this SAP to allow testing the primary endpoint, then secondary endpoint for the high dose first, then for the low dose while maintaining the type 1 error rate of 5% overall.

The sample size was re-calculated in Section 1.3.3 due to the change in the testing procedure stated above.

Section 2.2.1.3.2 was modified to allow longer time, up to 180 days, to observe the actual time for discharge or being ready to be discharged (NRD).

Section 2.2.1.7 was added for a sensitivity analysis using the baseline enteral feeding volume to break the tied NFE ranking.

Section 2.2.1.8 was added for a summary of number and percent of infants who achieve the complete and partial enteral feeding success for each treatment.

The reporting periods for AE reporting have been further defined in Section 2.3.2.1.

Section 3.1. The timing of the sample size re-estimation relevant to the futility analysis is further clarified. The conditional power is raised from 20% to 35%. Based on the conditional power and the totality of the clinical data available at the futility analysis, the DMC will recommend to continue or discontinue one or both dose arms. The sponsor will consider increasing the total sample size up to 450 patients based on the sample size

Confidential Page 37 of 40

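### SAP 3.1 supports its re-estimation power statement with 152 per arm (456 in total) under a cap of 450; the discrepancy is small, and the 5% dropout needs reconciling with SAP 1.3.3

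*SAP*

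**What the plan says.** SAP 3.1 sets the trigger and the ceiling for the re-estimation together: "The sample size may be increased up to 450 patients (total) if the estimated standard deviation is at least 10% larger" than the planning value. SAP section 4 repeats the ceiling: "The sponsor will consider increasing the total sample size up to 450 patients based on the sample size" re-estimation. SAP 1.3.2 randomizes to three groups at 1:1:1, so 450 is 150 per arm.

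The same paragraph of SAP 3.1 then gives the power argument. It begins "With 144 evaluable patients per arm, assuming a standard deviation of 5.0 days" and claims "85% power to detect a mean difference of 1.77 days"; for an SD of 4.0 the figure is 1.42 days. It applies a 5% dropout rate and concludes that "an enrollment of 152 patients per arm will likely recruit 144 per arm evaluable".

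SAP 1.3.3 derives the base size differently. The calculation gives 115 per group; then, to allow for missing data, "the sample size was increased to 130 per group or a total sample size of 390". No dropout rate is stated there.

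**The concern.** Two things in the SAP 3.1 paragraph do not fit together or do not fit the rest of the plan.

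- The enrolment behind the power statement exceeds the maximum that the paragraph itself allows, so the evaluable number and the detectable differences belong to a trial slightly larger than the one permitted.
- The paragraph allows 5% for dropout, whereas the base sample size for the same endpoint and test carries a missing-data allowance more than twice as large. No reason is given.

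What is at stake is the accuracy of the stated precision at the maximum size. SAP 3.1 also passes the sponsor's decision on sample size to the DMC as the main input to the futility assessment, and conditional power depends on the planned final size. The maximum and the assumptions behind it should therefore be unambiguous before the interim.

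**Working it through.** **Inputs.** Cap 450 in total (SAP 3.1 and 4); three arms at 1:1:1 (SAP 1.3.2); 152 enrolled and 144 evaluable per arm, 5% dropout, SD 5.0 and 4.0, differences 1.77 and 1.42 days, 85% power (SAP 3.1); two-sided 5% test for each dose (SAP 1.3.3); 115 raised to 130 per group (SAP 1.3.3).

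**Step 1: reproduce the plan's figures.**

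- Enrolment: 144 / 0.95 = 151.6, rounded up to 152; 152 × 0.95 = 144.4.
- Detectable difference, normal approximation: (z0.975 + z0.85) × SD × √(2/n) = (1.960 + 1.036) × SD × √(2/144). This gives 1.766 days at SD 5.0 and 1.413 at SD 4.0.
- Noncentral t: 1.772 and 1.417 days, matching the stated 1.77 and 1.42.

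The statement is internally correct for 152 enrolled per arm.

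**Step 2: compare with the cap.** 3 × 152 = 456, which is 6 above 450, or 2 per arm (2/150 = 1.3%).

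**Step 3: recompute at the cap with the stated 5%.** 450 / 3 = 150, and 150 × 0.95 = 142.5. Results by the noncentral t:

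| Evaluable per arm | Detectable, SD 5.0 | Detectable, SD 4.0 | Power for 1.77 days, SD 5.0 | Power for 1.42 days, SD 4.0 |
|---|---|---|---|---|
| 144 (as stated) | 1.772 | 1.417 | 84.9% | 85.1% |
| 143 | 1.778 | 1.422 | 84.7% | 84.9% |
| 142 | 1.784 | 1.427 | 84.4% | 84.6% |

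Rounding 142.5 down or up decides whether the SD 4.0 figure prints as 1.43 or 1.42. Either way the shift is about 0.01 day and about half a percentage point of power.

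**Step 4: sensitivity to the dropout allowance.** The step from 115 to 130 implies 1 − 115/130 = 11.5%. The protocol's own step in section 12.3, from 136 to 150, implies 1 − 136/150 = 9.3%. Applied at 150 per arm:

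| Allowance (back-calculated) | Evaluable per arm | Detectable, SD 5.0 | Detectable, SD 4.0 | Power for 1.77 days, SD 5.0 |
|---|---|---|---|---|
| 11.5% | 150 × 115/130 = 132.7, taken as 133 | 1.844 | 1.475 | 82.0% |
| 9.3% | 136 | 1.823 | 1.459 | 82.9% |

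These rows treat every infant with a missing result as contributing no information.

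**The case against.** The case for leaving the text alone is that the cap governs. It is stated in SAP 3.1, repeated in section 4, and 456 is never presented as a target. On this view 152 is an illustration, and 144 evaluable could still be reached from 150 per arm if dropout were 4% (1 − 144/150). Nothing changes in enrolment, the primary test, Type I error or the futility threshold. This stands, and it is why the point is minor. It does not remove the mismatch: the paragraph states 5%, and at 5% the cap does not yield 144.

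On dropout, the objection is that 5% is the only rate the sample-size text states. The 11.5% is inferred from a step that may include rounding, and a margin in the base size need not equal a rate used later. SAP 1.6.5 also imputes missing ranks, and infants with NEC or death are ranked under SAP 1.3.3 and 2.2.1.3.2, so infants without a result are not simply dropped from the test. This stands as far as it goes: the 133-per-arm figures are a sensitivity case and not a replacement for the stated ones. Against it, imputation keeps infants in the test without restoring the missing information, and the SAP itself inflates for missing data and counts evaluable patients. SAP 3.1 also makes provision for more than 10% missing at the interim, so losses above 5% are contemplated. The difference deserves an explanation.

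A reader might also infer that the DMC sets the increase from these power figures. SAP 3.1 does not say so. The trigger is the blinded pooled SD, the sponsor decides, and the DMC is told the decision. The sentences on 1.77 and 1.42 days illustrate power at two assumed SDs.

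**Conclusion.** The inconsistency is real and small. SAP 3.1 quotes an enrolment 6 infants above its own maximum. At the maximum, with the stated 5% dropout, about 142 per arm are evaluable, the 85% detectable differences are about 1.78 and 1.43 days, and power for the stated differences is about 84.4% to 84.6%. A reader might infer that the trial cannot deliver its stated power. The documents do not support that: the shortfall is one or two evaluable infants per arm.

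The unexplained change in dropout allowance could matter more. If the allowance implied by SAP 1.3.3 applied at the cap, power for 1.77 days at SD 5.0 would be about 82%. That would use about 3 of the 5 points by which the t-test target of 85% exceeds the 80% intended for the van Elteren test. This rests on a back-calculated rate and on counting imputed infants as lost. The detailed imputation text is not in the public copy, so the actual loss cannot be fixed from the documents.

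Severity: minor.

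**What to change.** Restate the SAP 3.1 paragraph at 150 enrolled per arm (450 in total), about 142 evaluable at 5% dropout, and detectable differences of 1.78 days (SD 5.0) and 1.43 days (SD 4.0) at 85% power.

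Add a sentence reconciling the 5% with the allowance behind 115 to 130 in SAP 1.3.3: either explain why a lower rate is expected, or use one allowance in both places. If the larger one is kept, the corresponding figures are about 133 evaluable and 1.84 and 1.48 days, with a note that they treat imputed infants as lost information.

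The cost is SAP wording, best settled before the interim. The design, conduct and tests do not change, and the stated figures become slightly less favourable.

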1.7 MULTIPLE COMPARISONS/MULTIPLICITY

This trial has one primary and one key secondary endpoint. The study is comparing each of two doses to placebo; a hierarchically ordered testing procedure will be used to test the primary endpoint, then secondary endpoint for the high dose first, then for the lower dose. Nutrinia believe that insulin as a growth factor will have effect with both doses. We expect that there is an opportunity for exploring higher dose that may yield a more favorable clinical effect than the lower dose that was used in the phase 2. Thus for that reason, a hierarchal approach is now being considered in the analysis. This procedure will preserve the type 1 error rate of 5% overall. The detailed testing procedure and the stopping rules are described below.

- 1. The NTRA $-2112\ 2000\ \mu\text{IU}$ Insulin/ml group is compared with the placebo group for the primary endpoint using a two-sided test at the 0.05 significance level.
 - If the null hypothesis is not rejected, no further comparisons are made.
 - If the null hypothesis is rejected, comparisons continue in the next step.
- 2. The NTRA $-2112\ 2000\ \mu\text{IU}$ Insulin/ml group is compared with the placebo group for the key secondary endpoint using a two-sided test at the 0.05 significance level.
 - If the null hypothesis is not rejected, no further comparisons are made.
 - If the null hypothesis is rejected, comparisons continue in the next step.
- 3. The NTRA $-2112\ 400\ \mu\text{IU}$ Insulin/ml group is compared with the placebo group for the primary endpoint using a two-sided test at the 0.05 significance level.
 - If the null hypothesis is not rejected, the final comparison will not be made.
 - If the null hypothesis is rejected, the final comparison in the next step will be made.
- 4. The NTRA $-2112\ 400\ \mu\text{IU}$ Insulin/ml group is compared with the placebo group for the key secondary endpoint using a two-sided test at the 0.05 significance level.

Confidential Page 18 of 40

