2.2 EFFICACY ANALYSES

2.2.1 Primary Efficacy Endpoint

2.2.1.1 Primary Analysis

The primary endpoint is the number of days to achieve enteral feeding of at least 150 ml/kg/day for at least 3 consecutive days (NFE). FAS will be used to test the primary efficacy endpoint. See Section 1.4 for explanation of how twins will be handled in this analysis.

For the primary endpoint, the following hypothesis will be tested:

- H₀: The distribution of the number of days to full enteral feeding is the same in the treated and the placebo groups.
- H₁: The distribution of the number of days to full enteral feeding differs in the treated and the placebo groups.

To maintain the overall study-wide two-sided Type I error rate at 0.05, a hierarchically ordered testing procedure, described in section 1.7, will be used.

Testing of the primary endpoint will be by the van Elteren test, stratified by gestational age group and region (North America, Europe, and Israel) with a threshold for statistical significance for each dose of P<0.05.

The average rank will be used for tied NFE values in SAS procedure above. The unique NFE values will retain the ranks as there was no ties.

The Hodges-Lehmann estimator will be used to estimate the treatment differences (each NTRA-2112 dose minus placebo) in days, and their 95% confidence intervals.

Confidential Page 23 of 40

Statistical Analysis Plan V1.3 SAP Date: 06APR2018

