3.2 DATA MONITORING COMMITTEE

An independent DMC is established and responsible for monitoring the trial to ensure the safety of patients in the trial. The DMC will review safety data and will make recommendations whether to continue or terminate the study. The DMC analyses and operations will be formally separated from the sponsor, the investigators, and the Steering Committee.

The DMC's responsibilities are to:

- Review safety and efficacy data during the study with consideration for the impact on patient safety, as well as the ethics of continued study conduct.
- Conduct review results of interim and final safety evaluations of the study, including an interim analysis for futility.
- Consider factors external to the study when relevant information becomes available, such as scientific or therapeutic developments that may have an impact on safety, scientific integrity, or the ethics of conducting the study.
- Review and evaluate ad hoc safety issues concerning the study that arise from any Serious Adverse Drug Reaction (an adverse event that might be related to the study drug, i.e. a causal relationship between exposure to the study drug and the serious adverse event is at least possible) or other safety matters at the request of the sponsor.
- Make recommendations to the sponsor concerning continuation/termination, or other modifications of the study based on the observed beneficial or adverse effects of the study drug.
- Operate according to the procedures described in the DMC charter.

A DMC Charter has been developed that defines the DMC organization, responsibilities, relationship with other trial entities, and the purpose and schedule of the DMC meetings.

Confidential Page 36 of 40

Statistical Analysis Plan V1.3 SAP Date: 06APR2018

The charter provides the procedures for ensuring confidentiality, proper communication, scopes of the interim data to be presented, and the statistical guidelines for interim futility analysis by the DMC.

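### The stated 85% / at least 80% power leaves out the 35% futility guideline; if followed, it cuts power to about 74–77% at 115 evaluable per arm, and the interim z is not tied to the final rank test

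*SAP*

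**What the plan says.** SAP 1.3.3 plans on 8.0 days for placebo and 6.6 for each active dose, SD 3.5, and a two-sided 5% test of each dose against placebo. It obtains 115 infants per group for 85% t-test power, expects at least 80% from the van Elteren test, and raises the number to 130 per group (390 in all) for missing data. SAP 3.1 repeats the 85% figure for 144 evaluable per arm in its re-estimation cases, where the total may rise to 450.

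SAP 3.1 places a futility look at 150 or more randomized infants. Its guideline reads "If the conditional power is less than 35% in either dose, continuing to enter infants in that dose group will be considered statistically futile". On the method it says "The conditional power will be calculated based on the observed interim trend of effect size, not the original expectation in the sample size calculation", with the z obtained by "treating the primary endpoint as a continuous variable, approximately following the normal distribution". The guideline does not bind the DMC: "The recommendation will be based on the conditional power and the totality of the clinical data available". The sponsor's sample-size decision "will be the primary driver in the futility assessment". SAP 3.2 says that the DMC charter contains "the statistical guidelines for interim futility analysis by the DMC".

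For the final analysis, SAP 2.2.1.1 states: "Testing of the primary endpoint will be by the van Elteren test, stratified by gestational age group and region". SAP 1.3.3 and 2.2.1.3.2 give NEC and death the worst ranks, at 29 and 30 days.

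**The concern.** Dropping a dose at the look removes some trials that would have ended in significance. Power with the guideline followed must therefore lie below the fixed-sample figure, and a 35% cut-off on the observed trend is demanding when little more than a third of the information may be in. A reader of the SAP would take 85% or 80% as the power of the design. A DMC asked to weigh an advisory rule needs to know how often that rule flags a dose that works, and the SAP does not say.

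The second issue is the interim statistic. Read plainly, SAP 3.1 describes a z on mean days. Codes of 29 and 30 are harmless in a rank test, where only order counts. In a mean-based z they are extreme values that inflate the SD. The interim figure could then disagree with the test it is meant to predict.

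**Working it through.** **Inputs.** Difference 1.4 days, SD 3.5, two-sided 0.05, and 115 or 130 per arm (SAP 1.3.3); look at 150 or more randomized, cut-off 35%, current trend (SAP 3.1). The SAP gives no information fraction t, so t is an assumption: 150/390 = 0.385, 50/115 = 0.435, or one half; 150/450 = 0.333 if the total becomes 450.

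**Reproducing the plan.** The normal formula 2 × (3.5/1.4)² × (1.960 + 1.036)² = 112.2 gives 113 per arm, and the exact t-test gives 114, against the stated 115. Exact t-test power at 115 is 85.6%. The two 144-per-arm cases give 84.9% (1.77 days, SD 5.0) and 85.1% (1.42 days, SD 4.0). The stated figures are correct.

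**Adding the guideline.** Conditional power under the observed trend is Φ[(Z_t/√t − 1.96)/√(1 − t)]. It falls below 35% when

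Z_t < c = √t × [1.96 + √(1 − t) × z₀.₃₅], with z₀.₃₅ = −0.385.

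This gives c = 1.028, 1.101, 1.193 and 0.950 at t = 0.385, 0.435, 0.5 and 0.333. With θ = (difference/SD) × √(n/2), the chance of a flag is Φ(c − θ√t). Power with the guideline followed is P(Z_t ≥ c and Z_1 > 1.96), bivariate normal with correlation √t. For n = 115, θ = 0.4 × √57.5 = 3.033; for n = 130, θ = 0.4 × √65 = 3.225.

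| Evaluable per arm | Look | No interim | Guideline followed | Effective dose flagged |
|---|---|---|---|---|
| 115 | 150/390 | 85.8% | 74.1% | 19.7% |
| 115 | 50/115 | 85.8% | 75.5% | 18.4% |
| 115 | half | 85.8% | 77.0% | 17.1% |
| 130 | 150/390 | 89.7% | 78.8% | 16.6% |
| 130 | half | 89.7% | 81.7% | 13.8% |
| 144 (either case) | 150/450 | about 85% | about 72% | about 22% |
| 144 (either case) | half | about 85% | about 76% | about 17–18% |

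For comparison, the 20% cut-off in Protocol 12.4.12 would give 78.1–80.5% at 115 for t from 0.385 to 0.5.

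**On the van Elteren scale.** Trials were simulated (8,000 per setting) in whole days, with normal or gamma data, six equal strata without stratum effects, and no NEC or deaths. At 115, power without an interim is 82–91%, so the 80% expectation holds. With the guideline it is 71–77% (150/390) or 75–79% (half information). At 130, 86–94% falls to 76–82% or 80–83%.

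**Two doses, both fully effective, 115 per arm, shared placebo.** At least one dose is flagged 31% (150/390) or 27% (half information) of the time. Both primary tests are significant with neither dose flagged in roughly 60–64% of trials, against 77% with no interim. SAP 1.7 tests high-dose primary, high-dose key secondary, then low-dose primary, and at each of the first two steps "If the null hypothesis is not rejected, no further comparisons are made". If a dropped high dose counts as not rejected, the 60–64% is therefore an upper limit for the low dose's primary claim.

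**NEC and death in the interim z (illustration only).** The rates below are assumed equal in every arm. Half the events are coded 29 and half 30, added to data with SD 3.5, at 130 per arm with the look at 150/390.

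| Assumed rate | Total SD | Effective dose flagged, z on days | Flagged, van Elteren Z |
|---|---|---|---|
| 1% | about 4.1 | 25–26% | 14–20% |
| 2% | about 4.7 | 33% | 16–21% |
| 5% | about 5.9 | 45–46% | 19–24% |

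If the total SD is instead held at 3.5 with a 1% rate, the z on days flags 17% and the rank Z 6–9%.

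**The case against.** **No stated figure is wrong, and the rule is advisory.** Both are true. The loss applies only as far as the DMC follows the guideline, and the unseen charter may already give the DMC these figures. The SAP still reports power without them.

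**The 115 case is pessimistic.** It assumes that the whole missing-data allowance is lost, while the SAP imputes missing ranks and elsewhere assumes 5% dropout. At 130 × 0.95 = 123.5 per arm, power with the guideline is 76.9–79.8%. At 130 with the look at half information, the simulated van Elteren power of 80–83% still meets the 80% expectation. This is why a range is needed, but 115 is the plan's own evaluable number.

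**The interim z might be rank-based.** SAP 3.1 gives no formula, its data transfer includes the two stratification factors, and the text of 2.2.1.3.1 is not visible. The strata would suit a stratified analysis of days equally well, and the continuous, approximately normal wording points to means. What stands is that the text is ambiguous.

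**The NEC/death illustration rests on assumed rates and ignores re-estimation.** All three total SDs exceed the 10% trigger (3.5 × 1.10 = 3.85), so the total could rise to 450 before the futility review. Using that boundary lowers the flag rates for the z on days by only about 3 points, to roughly 23%, 30% and 43%.

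**Conclusion.** The concern holds. With the planned effect and SD and the guideline followed, per-comparison power is about 74–77% at 115 evaluable per arm and 79–82% at 130, a loss of roughly 8 to 12 points. A fully effective dose is flagged about 14–20% of the time under the 390 plan, and about 22% if the total becomes 450 and the look stays at 150. These figures assume mechanical adherence and a look at between 38% and 50% of the information (33% in the 450 case). The second part is a gap in specification: the SAP does not fix the interim statistic or the handling of NEC and death within it. The size of any mismatch depends on event rates that the documents do not give. Type I error and the validity of the final test are not affected. This should be fixed, but it does not threaten the trial's conclusions.

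**What to change.** 1. **SAP 3.1.** Compute conditional power for each dose from the interim van Elteren Z, with the strata of the final test and the NEC/death ranking of 1.3.3 and 2.2.1.3.2. If a z on days is kept, give its formula and state how NEC and death enter it.
2. **SAP 1.3.3 and 3.1.** Beside the fixed-sample figures, state the per-comparison power with the guideline followed, as a range over interim timing: about 74–77% at 115 evaluable and 79–82% at 130 on the t-test basis, with the van Elteren figure from simulation. Give the matching figures for the 450 case. State the chance of flagging a fully effective dose, and make sure the DMC has it if the charter does not already provide it.

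The cost is SAP wording and one simulation. Enrolment, data collection, the final test and the 35% cut-off, which is the sponsor's choice, do not change. The first change has a small price when data are normal with no NEC or deaths: the rank Z flags an effective dose slightly more often (24% against 21% at 115; about 19% against 17–18% at 130). With gamma-shaped data it flags less often (13% against 16% at 130). The second change puts a less favourable figure beside the stated one.
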